9.1 Definition of Response

Response and progression will be evaluated in this study using the ACTG response criteria.

9.1.1 Complete response: CR is defined as the absence of any detectable residual disease, including tumor-associated edema, persisting for at least 4 weeks. In participants, in whom pigmented (brown or tan) macular skin lesions persist after apparent CR, biopsy of at least one representative lesion is required in order to document the absence of malignant cells. In participants known to have had visceral disease, an assessment at restaging with appropriate endoscopic or radiographic procedures should be made.

9.1.2 Partial response (PR) is defined as no new lesions (skin or oral), or new visceral sites of involvement (or the appearance or worsening of tumor-associated edema or effusions); AND

- A 50% or greater decrease in the number of all previously existing lesions lasting for at least 4 weeks; OR
- Complete flattening of at least 50% of all previously raised lesions (i.e., 50% of all previously nodular or plaque-like lesion become macules); OR
- A 50% decrease in the sum of the products of the largest perpendicular diameters of the marker lesions.

Note: Participants with residual tumor-associated edema or effusion who otherwise meet the criteria for complete response will be classified as having a PR.

9.1.3 Stable disease is defined as any response not meeting the criteria for CR, PR, or

progressive disease.

9.1.4 Progressive disease (PD) is defined as follows:

For participants with ≤ 50 cutaneous lesions

- 25% increase in the sum of perpendicular diameters of the indicator lesions, OR
- $\geq 25\%$ increase in the total lesion count, or a minimum of 5 new lesions, whichever is greater, OR
- $\geq 25\%$ increase in the number of raised lesions (minimum of 5 new raised lesions if there are very few raised lesions, for example ≤ 8), whichever is greater.

Note: There are body sites where disease is particularly difficult to evaluate, and a few new lesions may be counted in spite of the fact that a participant is not actually progressing. For example, lesions of the foot, particularly those which are flat, are difficult to evaluate because their intensity may be variable based on how much edema is present, how much the person walked the day before, how long their feet have been in a dependent position prior to the physical exam, etc.

For participants with > 50 cutaneous lesions

- $\geq 25\%$ increase in the sum of the perpendicular diameters of the indicator lesions, OR
- $\geq 25\%$ increase in the total number of lesions in the prospectively defined anatomic sites containing representative numbers of lesions, OR
- A total of 5 new lesions in anatomic sites which were previously documented as having no evidence of cutaneous disease on the whole-body diagram, OR
- $\geq 25\%$ increase in the number of raised lesions (minimum of 5 raised lesions if there are very few raised lesions, for example < 8) whichever is greater. Photographic documentation of “gross” or significant progression, particularly in areas that were not being followed, will be of particular value.

In order to classify a response as PR, the participant must have at least a PR in either the cutaneous or non-cutaneous sites of disease, and no evidence of progression as defined in the above criteria. In order to classify a response as a CR, the participant must have a CR in both the cutaneous (if applicable) and non-cutaneous (if applicable) sites of disease, and no evidence of progression as defined by the above criteria.

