10.2 Sample Size/Accrual Rate

A total of 20 evaluable participants will be enrolled. The design was developed by considering the joint probability of clinical response and toxicity simultaneously (Jin H. Alternative designs of phase II trials considering response and toxicity, *Contemp Clin Trials* 28 (2007): 525-53). The null hypothesis for defining the unacceptable region based on clinical response rate and toxicity rate simultaneously and the alternative hypothesis for defining the region for a promising agent are as follows:

- $H_0: P_{\text{resp}} \leq 0.30 \text{ OR } P_{\text{tox}} \geq 0.30$
- $H_1: P_{\text{resp}} \geq 0.60 \text{ AND } P_{\text{tox}} \leq 0.10$

In a single stage design, 20 participants will be evaluated for clinical response and toxicity. Toxicity will be defined as: unacceptable toxicities as defined in [Section 10.1](#). All unacceptable toxicities that are possibly, probably, or definitely attributed to protocol therapy will be counted as a toxicity.

The null hypothesis will be rejected if there are at least 9 responders, and no more than 3 participants who experience unacceptable toxicities. This design has power of 0.82 and a significance level of 0.11. The planned accrual rate will be one participant per month.

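### Two of the three partial-response routes carry no 4-week duration, so one open-label site reading can count as a response on the primary endpoint

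*Combined protocol and SAP*

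**What the plan says.** Section 9.1.1 requires a complete response to persist for 4 weeks. Section 9.1.2 requires the absence of new lesions, new visceral sites and worsening edema or effusion, and then any one of three routes:

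- lesion count: "A 50% or greater decrease in the number of all previously existing lesions lasting for at least 4 weeks";
- flattening: "Complete flattening of at least 50% of all previously raised lesions";
- marker-lesion area: "A 50% decrease in the sum of the products of the largest perpendicular diameters of the marker lesions".

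Only the first states a duration. Sections 9.1.7 and 9.1.9 date response from its first documentation, and no section asks for a confirmatory reading.

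Under Section 9.0, response is read by physical examination on Day 1 of every cycle (±3 days). Site physicians or advanced practice clinicians may do the reading. The trial is open label (7.2.1) and lasts up to 12 cycles. Section 9.0 takes the primary response rate after two or more cycles. Section 10.1 takes it after at least two cycles and reports later cycles separately.

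Section 10.2 sets the test: "In a single stage design, 20 participants will be evaluated for clinical response and toxicity". The null is a response rate of at most 0.30 or a toxicity rate of at least 0.30. It is rejected with at least 9 responders and at most 3 participants with unacceptable toxicity. The stated power is 0.82 and the stated level 0.11.

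**The concern.** Complete or partial response is the efficacy half of the primary endpoint. It is compared with a fixed historical rate, so there is no control arm in which the same reading error would cancel. With the duration missing from two routes, a transient or mistaken reading by flattening or marker area makes a responder, even if the next visit does not bear it out. No blinded or independent review is described.

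The number of chances is also open. If any visit after two cycles can supply the response, each further visit is another opportunity for a false one. The response cut-off is sensitive to small shifts: the chance of at least 9 of 20 is 0.113 at a counted rate of 30%, 0.238 at 35% and 0.404 at 40%.

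**Working it through.** **Inputs from Section 10.2:** n = 20; at least 9 responders; at most 3 toxicities; null rates 0.30 and 0.30; alternative rates 0.60 (response) and 0.10 (toxicity).

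**Reproducing the plan's figures** (exact binomial, response and toxicity taken as independent):

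- Power = P(X ≥ 9 | 20, 0.60) × P(T ≤ 3 | 20, 0.10) = 0.9435 × 0.8670 = 0.818. The plan states 0.82.
- Level = the larger of P(X ≥ 9 | 20, 0.30) = 0.113 and P(T ≤ 3 | 20, 0.30) = 0.107, so 0.113. The plan states 0.11.

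The design is correctly computed. The question is what rate of counted response enters it.

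**Assumptions, none of them in the documents:** 30% of participants truly and durably respond. In each of the other 70%, every counted visit gives a false partial response with probability f, independently, with f between 0.01 and 0.03. The number of counted visits is k.

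**One reading suffices** (flattening and marker routes as written):

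- False responder probability x = 1 − (1 − f)^k
- Counted rate p = 0.30 + 0.70x
- Response-side error = P(X ≥ 9 | 20, p)

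| k | x | p | P(at least 9 of 20) |
|---|---|---|---|
| 1 | 0.010 to 0.030 | 0.307 to 0.321 | 0.13 to 0.16 |
| 5 | 0.049 to 0.141 | 0.334 to 0.399 | 0.19 to 0.40 |

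**Two consecutive readings required:**

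- One early reading plus its confirmation: x = f² = 0.0001 to 0.0009, giving 0.113 to 0.115.
- Five visits: x = 1 − [(1−f)^5 + 5f(1−f)^4 + 6f²(1−f)³ + f³(1−f)²] = 0.0004 to 0.0035, so p = 0.3003 to 0.3025, giving 0.114 to 0.118.

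**Scope:** these are response-side probabilities. At a true toxicity rate of 10%, multiply by 0.867 for the joint rule. The no-error value becomes 0.098, the one-reading range 0.111 to 0.138, and the five-reading range 0.17 to 0.35.

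**The ±3-day window:** nominal Day 1 visits are 28 days apart. A first reading 3 days late and a second 3 days early are 28 − 6 = 22 days apart, which is short of 4 weeks.

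**The case against.** Much can be said for the plan. Under 8.1.9, marker lesions are the largest with clear margins. Appendix VI has them photographed with a millimeter ruler and photographs repeated when the response category changes. That leaves a record, but no one is required to read it a second time. The note in 9.1.4 on hard-to-read sites concerns progression. Spurious new lesions would block a partial response, so that note is not evidence of inflation.

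The error rate, the five visits and the independence are all assumed. Section 10.1 reports later cycles separately, so the primary response may rest on one early reading, where the effect is modest. A misreading that the same assessor repeats would pass confirmation too. All of this limits the size; none of it supplies the missing duration.

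A reader might infer two stronger faults, and the documents do not support either.

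- *That the new-lesion and progression rules contradict each other and so create responders.* Section 9.1.2 bars new lesions, while the closing paragraph of 9.1.4 says "the participant must have at least a PR in either the cutaneous or non-cutaneous sites of disease, and no evidence of progression". The second condition adds to the definition and does not replace it. In skin-only disease, adequate shrinkage with a few new lesions, short of progression, is stable disease under 9.1.3. Barring new lesions also makes a partial response harder to reach. What remains is narrow: a non-cutaneous partial response with a few new skin lesions can be classed two ways.
- *That the differing size measures inflate response.* Partial response uses products of diameters, while progression uses "25% increase in the sum of perpendicular diameters of the indicator lesions". The difference can move participants between stable and progressive disease, and both are non-response.

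**Conclusion.** The point holds for the missing duration. As written, one unblinded site reading by flattening or marker area counts as a response on the primary endpoint, and this can inflate the response rate against the fixed 30% null.

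Under the stated assumptions, the response-side error rises from 0.113 to 0.13-0.16 with one counted reading and to 0.19-0.40 with five. Two consecutive readings hold it at 0.113-0.118. It would be wrong to infer that the trial's actual error is 0.40: that is the top of an illustrative range. Correlated readings would shrink both the inflation and the protection that confirmation gives. The textual gap itself rests on no assumption.

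The sample size, the 9-of-20 rule and the stated error rates need no change.

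**What to change.** 1. Move the 4-week persistence requirement into the opening sentence of 9.1.2 so that it covers all three routes, and require confirmation at the next scheduled Day 1 assessment.
2. State how the ±3-day window counts toward 4 weeks, since consecutive readings may be as little as 22 days apart.
3. Fix which visits count for the primary response, and make Sections 9.0 and 10.1 agree on this.
4. Separately, reconcile 9.1.2 with the closing paragraph of 9.1.4 for a non-cutaneous partial response with a few new skin lesions. Also reconcile the size measures used for partial response and for progression. No progression threshold is proposed here, because progression governs removal from treatment under Section 4.5.

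**Cost:** protocol wording. Assessments already fall every 28 days, so no visits are added. The response rate may be slightly lower because some true but brief responses would no longer count. As an illustration, if the alternative rate fell from 0.60 to 0.57, the joint power would go from 0.82 to 0.78; at 0.55 it would be 0.75.

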9.1.5 Non-cutaneous progression

Progressive disease includes new visceral sites of involvement or progression of visceral disease or the development of new or increasing tumor-associated edema or effusion lasting at least 1 week, which interferes with the participant’s normal activities. Progressive visceral disease, for measurable and evaluable disease, should be analogous to non-KS response criteria.

9.1.6 Recurrent disease

Recurrent disease is defined as the appearance of tumor following documentation of a complete remission.

9.1.7 Time to response

Time to response is defined as time from the first dose of chemotherapy until documentation of first response.

9.1.8 Time to progression

Time to progression is defined as time from initiation of chemotherapy to documentation of first progression.

9.1.9 Response duration

Response duration is defined as the time from first documentation of response to documentation of first progression.

10.0 STATISTICAL CONSIDERATIONS

10.1 Study Design and Endpoint

This is a multi-institutional, Phase II single-agent trial of sEphB4-HSA in participants with KS. Participants will be administered sEphB4-HSA via intravenous infusion. Each cycle of sEphB4-HSA will be 28 days (4 weeks). Each cycle of the study drug includes administration of 2 doses of sEphB4-HSA at 10 mg/kg administered on Days 1 and 15. The primary endpoint simultaneously evaluates clinical response and toxicity after a minimum of 2 cycles of therapy with sEphB4-HSA in participants with KS. Participants may continue on study protocol as long as their KS is continuing to respond or is clinically stable on study medication for up to 12 treatment cycles. If CR is achieved, the participant will receive one cycle beyond CR. Treatment may be resumed if KS progresses off treatment after a CR. The participant will resume the previous dose that he/she was receiving when CR was achieved. Participants who achieve PR or SD may continue the treatment at the dose he/she was receiving when PR or SD was achieved, for a maximum of 12 Cycles, if the participant and treating physician feel that it is beneficial to continue treatment. Treatment will be discontinued if the participant develops unacceptable toxicity or develops one of the protocol-defined reasons for treatment discontinuation. Participants who show PR or better disease will be followed every 3 months for up to 1 year, or until an earlier time of disease progression requiring additional treatment. All participants will be followed for 4 weeks after treatment completion.

All participants who receive any amount of the study drug will be evaluable for toxicity. Toxicities will be tabulated by type and grade, according to dose cohort. Toxicity will be based on CTCAE version 5.0.

Unacceptable toxicities include all of the below which are deemed to be *at least probably* attributed to the study drug:

- Grade 4 hematological toxicity (thrombocytopenia, neutropenia on growth factor) that lasts > 4 weeks
- Steven-Johnson Syndrome
- Major allergic reaction which requires epinephrine
- Grade 4 non-hematological toxicity that does not resolve with optimal supportive care (e.g., fluids, electrolyte replacement, anti-diarrheal and titration of antihypertensive medications)
- Grade 3 neuropathy for at least 4 weeks

Primary endpoint analysis plan

The observed proportions of participants experiencing clinical response and unacceptable toxicity will be calculated, as well as 95% confidence intervals. This will be done for the primary endpoint related to clinical response and unacceptable toxicity after a minimum of 2 cycles of therapy at the 10 mg/kg every two weeks dose level, and separately for response and toxicity at later cycles. Participants treated prior to version 4 dosed at 15 mg/kg every two weeks (n=3) will be combined with those treated at the revised dose level in analyses; a sensitivity analysis excluding these participants will also be performed to investigate the

impact of these participants on the primary outcomes. Adverse events will be tabulated according to type and severity. The Kaplan-Meier method will then be used to estimate the distribution of time to response, time to relapse, and time to death. Time to response is defined as time from the first dose of treatment until documentation of first response. Time to progression is defined as time from initiation of chemotherapy to documentation of first progression. Response duration is defined as the time from first documentation of response to documentation of first progression.

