2.3.8 Dosing in clinical trial

A phase I trial in refractory/relapsed solid tumors has been completed. The following dose levels were tested in the phase I trial: 2.5 mg/kg, 5 mg/kg, 10 mg/kg and 15 mg/kg administered weekly on Days 1, 8, 15, and 22; and 10 mg/kg, 15 mg/kg and 20 mg/kg administered every 14 days (2 weeks) on Days 1 and 15, by I.V. infusion for 60 minutes. The weekly dosing schema and schedule was chosen based on safety of weekly dosing in animal studies of doses up to 30 mg/kg. No DLTs were seen in this weekly dosing, however dose accumulation was noted. Cohorts consisting of 10 mg/kg, 15 mg/kg and 20 mg/kg, with administration every 14 days (2 weeks), were added to the phase I trial, given the dose accumulation noted with weekly dosing. The phase I maximum tolerated dose (MTD) has been reached with 2 of 6 participants, at 20 mg/kg administered every 14 days,

experiencing grade III hypertension that was not responsive to therapy, requiring dose reduction to 15 mg/kg every two weeks, and long half-life of 7 - 10 days. Therefore, the dose of 15 mg/kg every 2 weeks, administered on Days 1 and 15, was initially used as the starting dose in this Phase II trial.³¹

Based on updated data (unpublished communication with VasGene, 8/2018) from other trials with sEphB4-HSA (ClinicalTrials.gov ID NCT03146871), which take into consideration rates of hypertension and drug accumulation, other trials have been modified to use a dose of sEphB4-HSA of 10 mg/kg every 2 weeks. Based on this information combined with initial experience in this study, this trial is amended with protocol version 4.0 to use a dose of 10 mg/kg every 2 weeks, administered on Days 1 and 15 of each cycle. In addition, other unpublished studies (ClinicalTrials.gov ID NCT02717156 and NCT03049618), which dosed sEphB4-HSA at 10 mg/kg weekly, showed grade 3/4 hypertension in 3/21 and 3/19 participants, respectively. Given the updated information of drug accumulation in the context of an approximately 5-day half-life of sEphB4-HSA, the weekly dose will not be used in this trial.

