In the case of grade 3 hypertension as documented by two or more different measurements - that are at least 30 minutes apart and measured by a healthcare provider - treatment with sEphB4-HSA must be held until hypertension returns to target BP (<140/90 mm Hg). Participants should be initiated on antihypertensive therapy, or if already on antihypertensive therapy, participants should have their antihypertensive therapy titrated, per the treating physician. BP should be rechecked 3-5 days after initiation or titration of antihypertensive therapy, or after approximately 5 half-lives to allow antihypertensive drug levels to achieve steady state (~5 days for an antihypertensive dosed daily and ~3 days for one dosed twice daily). If SBP is still ≥ 140 mm Hg and/or DBP is ≥ 90 mm Hg, the antihypertensive dose should be increased, or additional antihypertensive therapy added as indicated. Continue to monitor BP and titrate antihypertensives every 3-5 days until target BP (<140/90 mm Hg) is achieved. sEphB4-HSA should be held until hypertension returns to target BP (<140/90 mm Hg) and patient is asymptomatic, at which point sEphB4-HSA

[figure not shown]
treatment can be resumed.

If after subsequent dosing of sEphB4-HSA, grade 3 hypertension recurs - as documented by two or more different measurements that are at least one hour apart and measured by a healthcare provider - hold sEphB4-HSA and titrate antihypertensives as above until target BP (<140/90 mm Hg) is achieved. When subsequent dosing of sEphB4-HSA is restarted, patient will require reduction of sEphB4-HSA by one dose level.

If patient has to hold treatment for 4 weeks due to hypertension, sEphB4-HSA treatment will be discontinued.

All participants must be educated about the hypertension side effect and instructed to contact the study team if their BP remains under poor control between visits. It is recommended participants keep a BP log, but this is up to the treating physician's discretion.

Hypertension Management Schema

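### Read literally, the toxicity list behind the 3-of-20 rule counts neither drug-related grade 5 events nor the treatment-unresponsive grade 3 hypertension that set the phase I MTD

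*Combined protocol and SAP*

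**What the plan says.** Section 10.2 takes its definition from Section 10.1: "Toxicity will be defined as: unacceptable toxicities as defined in" that section. Section 10.1 opens its list with "Unacceptable toxicities include all of the below which are deemed to be", sets probable attribution as the minimum, and gives five items, here in a different order:

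- "Grade 4 non-hematological toxicity that does not resolve with optimal supportive care (e.g., fluids, electrolyte replacement, anti-diarrheal and titration of antihypertensive medications";
- Stevens-Johnson syndrome;
- an allergic reaction severe enough to need epinephrine;
- grade 4 blood-count toxicity lasting more than 4 weeks;
- "Grade 3 neuropathy for at least 4 weeks".

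No item names grade 5 or death, and neuropathy is the only grade 3 item. Section 10.2 sets a lower attribution threshold than 10.1, because it also counts events possibly due to treatment.

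On hypertension, Section 2.3.8 reports: "The phase I maximum tolerated dose (MTD) has been reached with 2 of 6 participants, at 20 mg/kg administered every 14 days". It describes those two participants as "experiencing grade III hypertension that was not responsive to therapy". Section 5.4 says: "If patient has to hold treatment for 4 weeks due to hypertension, sEphB4-HSA treatment will be discontinued". Section 4.5 also lists uncontrolled sustained hypertension as a reason for removal. Section 9.0 limits the primary toxicity endpoint to the first two cycles.

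On death, Section 10.7 has a category for early death from toxicity and scores it as treatment failure in the response analysis. The accrual hold in Sections 4.1 and 5.1 covers grades 4 and above, but apart from major bleeding only for unexpected events.

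**The concern.** The primary objective is response and toxicity together, and the count against 3 of 20 is the only numerical toxicity criterion in the statistical section. A participant could die from the drug, or be stopped permanently for grade 3 hypertension that antihypertensives did not control, and add nothing to that count. The first is a counting error that nobody would intend. The second matters because this is the event that limited dose in phase I, and Section 2.3.8 gives hypertension rates as one reason for lowering the dose. A reader who sees the toxicity limb passed would naturally assume that both had been taken into account.

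**Working it through.** **1. The plan's own figures.** Inputs from Section 10.2: n = 20; success if responders R ≥ 9 and toxicities T ≤ 3; null rates 0.30 (response) and 0.30 (toxicity); alternative rates 0.60 and 0.10.

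- Power, taking response and toxicity as independent: P(R ≥ 9 | 20, 0.60) × P(T ≤ 3 | 20, 0.10) = 0.9435 × 0.8670 = 0.818. The plan states 0.82. Over the full range of within-participant dependence it is 0.812 to 0.832.
- Significance level, the larger of the two boundary errors: P(R ≥ 9 | 20, 0.30) = 0.1133 and P(T ≤ 3 | 20, 0.30) = 0.1071. The maximum is 0.113. The plan states 0.11.

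Both figures reproduce. The arithmetic is sound; the question is what T counts.

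**2. Events set against the list.**

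| Drug-related event | Counted under 10.1, read literally? |
|---|---|
| Grade 4 hypertension not resolved by titration | Yes |
| Grade 3 hypertension unresponsive to therapy | No |
| Grade 3 hypertension ending treatment after a 4-week hold (5.4) | No |
| Grade 5 event | Not as such; only through a listed event that came before it |

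The phase I rate was 2/6 = 0.333 (exact 95% CI 0.04 to 0.78). On this list, the event that set the MTD would score 0 of 6.

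**3. Effect on the count.** Each omitted participant lowers T by one against a limit of 3. As a hypothetical case, two listed toxicities and two drug-related deaths give T = 2 (pass) as written and T = 2 + 2 = 4 (fail) if deaths count. The response limb does not make up for this: it needs 9 of 20 responders, so it tolerates 20 − 9 = 11 non-responders for any reason.

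**4. Cost of moving hypertension into the primary rule.** Let p be the total counted toxicity rate, all listed events plus the added one. Then P(T ≤ 3) = Σ C(20,k) p^k (1 − p)^(20−k) for k = 0 to 3. Joint power is this times 0.9435, with response rate 0.60 and independence.

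| Assumed p | P(T ≤ 3) | Joint power |
|---|---|---|
| 0.10 (design) | 0.867 | 0.818 |
| 0.143 (3/21) | 0.682 | 0.644 |
| 0.158 (3/19) | 0.609 | 0.575 |
| 0.20 | 0.411 | 0.388 |

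The rates 3/21 and 3/19 are from Section 2.3.8. They cover all grade 3/4 hypertension at 10 mg/kg weekly and do not say how many cases were unresponsive. They serve only as a range.

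**The case against.** The hypertension threshold looks deliberate. The grade 4 item names antihypertensive titration, so its authors had hypertension in mind. Section 5.4 treats grade 3 hypertension as expected and manageable: hold, titrate, resume. Where to set the bar for an unacceptable event is partly judgement. This stands, and it is why hypertension belongs in a supporting analysis unless the sponsor chooses otherwise. It explains leaving out controlled grade 3 hypertension better than it explains leaving out the unresponsive form.

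The events would also be visible elsewhere. Adverse events are tabulated by type and grade, removal reasons are recorded, and deaths need expedited reporting. This stands too: the gap is in the primary decision rule, not in safety monitoring.

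The list's opening verb may be read as non-exhaustive, and a death might be counted through an unresolved grade 4 event before it. The text says neither. If the list is open, the count of 3 has no fixed definition, which also needs repair.

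A reader might infer that the test cannot see hypertension at all, or that the toxicity limb would pass with probability 1.0 where it should pass with 0.107. The documents do not support either. Unresolved grade 4 hypertension counts. The 1.0 comes from assigning 30% to an uncounted event and nothing to any counted one. The nearest observed rate, 2/6, arose at 20 mg/kg every 14 days, twice the current dose, and no rate is given for 10 mg/kg every 2 weeks.

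**Conclusion.** The point holds in a limited form. Read literally, the Section 10.1 list leaves out drug-related grade 5 events; this is a drafting gap that would give a wrong count and should be closed. The list also leaves out grade 3 hypertension unresponsive to therapy. That is a real gap in what the primary toxicity conclusion covers, but partly a choice of threshold.

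The stated power and significance level are correct for the events listed and give no assurance about those left out. How far the omission would change this trial's result cannot be computed, because the rate of unresponsive hypertension at the current dose is not in the documents. A reader might also infer that adding hypertension to the rule costs little. That depends on the rate: if total counted toxicity were 14 to 16%, joint power would be about 0.57 to 0.64 instead of 0.82.

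**What to change.** 1. **Grade 5.** Add to the Section 10.1 list any grade 5 event that meets the attribution threshold. First reconcile that threshold: 10.1 requires at least probable attribution, and 10.2 also accepts possible.

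2. **Hypertension.** Keep the limit of 3 in 20 as the primary rule. Pre-specify a supporting analysis that repeats the toxicity count and its 95% confidence interval, also counting participants permanently discontinued for treatment-unresponsive hypertension of grade 3 or higher with onset in the first two cycles. Using onset settles the case of a hold that begins in cycle 2 and ends after it.

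3. **Reconcile first.** The sponsor must align the hypertension removal criteria in Sections 4.5 and 5.4 before this count can be defined. Section 4.5 removes participants for sustained readings above 140 and 90 despite medication. These overlap the grade 2 band in 5.4, where treatment may continue.

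4. **State the limit.** Say that the primary toxicity conclusion does not cover unresponsive grade 3 hypertension, unless the sponsor adds it to 10.1 and re-justifies the 0.10 and 0.30 rates for the wider definition.

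Cost: one list item, one supporting analysis and a sentence on interpretation. Adverse event grade and reason for removal are already collected. The toxicity count may rise, and joint power falls as shown if hypertension enters the primary rule. Section 6.3.3 attaches a reporting deadline to unacceptable toxicities, but deaths already need expedited reporting. No change to how any participant is treated is proposed.
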